13. LIST OF PLANNED FIGURES

Grouping	Title
Efficacy	Kaplan-Meier Plot of Progression Free Survival (centrally assessed)
	Kaplan-Meier Plot of Overall Survival
	Kaplan-Meier Plot of Progression Free Survival (locally assessed)
	Kaplan-Meier Plot of Duration of Response
	Kaplan-Meier Plot of intervention for CNS disease

14. LIST OF PLANNED DATA LISTINGS

Grouping	Title
Disposition	Listing of Screen Failures
Demography	Listing of Demographics and Baseline Characteristics
Medical History	Listing of Medical History
Cancer History	Listing of Prior Cancer History
	Listing of Prior Cancer Therapies
Concomitant Medications	Listing of Concomitant Medications
	Listing of Non-Pharmacologic Anti-Diarrheal Treatments
Study Medication	Listing of Test Article Administration
	Listing of Subjects with Dose Reduction
	Listing of Subjects with Dose Hold
Efficacy	Listing of Tumor Data (centrally assessed)
	Listings of Tumor Measurements and Assessments
Health Outcomes	Listing of EORTC QLQ C30 and BR23 data
	Listing of EQ-5D data
Safety	Listing of Adverse Events
	Listing of Adverse Events with Toxicity Grade 3 or higher
	Listing of Treatment Emergent Adverse Events with Toxicity Grade 3 or higher
	Listing of Drug Related Adverse Events
	Listing of Serious Adverse Events
	Listing of Adverse Events Leading to Treatment Discontinuation
	Listing of Adverse Events Leading to Dose Reduction
	Listing of Adverse Events Leading to Dose Hold
	Listing of Drug Related Adverse Events
	Listing of Deaths
	Listing of potential Hy's law cases
Diarrhea	Listing of Treatment Emergent Diarrhea by Severity
	Listing of Treatment Emergent Diarrhea Grade 3 or Higher
	Listing of Anti-diarrheal Medications
Laboratory	Listing of Laboratory Data

Grouping	Title
Vital Signs	Listing of Vital Signs Data
	Frequency Table of Potentially Clinically Significant Vital Signs Data
Physical Exam	Listing of Physical Examination Data
ECG	Listing of ECG Data
LVEF	Listing of LVEF Data

HOA	Health Outcomes Assessment
KM	Kaplan-Meier
OS	Overall Survival
PFS	Progression-free Survival
QLQ-C30	European Organization for Research and Treatment-QOL questionnaire
QOL	Quality of Life
SAP	Statistical Analysis Plan
TTD	Time to Deterioration
UK	United Kingdom

1. INTRODUCTION

This supplemental Statistical Analysis Plan (SAP) is intended to further describe the efficacy analysis for the secondary endpoints of Health Outcomes Assessments (HOA) and Central Nervous System (CNS) as well as some additional sensitivity analyses.

For the purposes of this supplemental SAP we will use the term Quality of Life (QoL) to cover all the analysis relating to the Health Outcomes Assessments (HOA).

2. ANALYSIS OF QUALITY OF LIFE DATA

This section expands on the QoL analysis described in sections 8.3.3.1-8.3.3.2 of the Statistical Analysis Plan (SAP) version 2.1.

In summary, there were three Quality of Life (QoL) instruments used in the NALA study: QLQ-C30, BR-23, and EQ-5D-5L. There are 26 scales in these instruments and they are presented in [Table 1](#) (QLQ-C30: 16 scales, BR-23: 8 scales, VAS and EQ-5D-5L health index score). The HOA instruments are administered every 2 cycles (6 weeks) until the end of study drug administration.

Table 1: Quality of Life Instruments and Scales

	Scale	Number of items	Score Range	Version 3.0 Item Numbers	Function or Symptom Scales	
QLQ-C30 Summary Score	C30Sum	13	0-100	1-28, 30	F	QLQ-C30
Global Health status/QoL						
Global health status/QoL	QL2	2	0-100	29, 30	F	QLQ-C30
Functional Scales						
Physical functioning	PF2	5	0-100	1 to 5	F	QLQ-C30
Role Functioning	RF2	2	0-100	6,7	F	QLQ-C30
Emotional Functioning	EF	4	0-100	21 to 24	F	QLQ-C30
Cognitive Functioning	CF	2	0-100	20, 25	F	QLQ-C30
Social Functioning	SF	2	0-100	26, 27	F	QLQ-C30
Symptom Scales						
Fatigue	FA	3	0-100	10, 12, 18	S	QLQ-C30
Nausea and vomiting	NV	2	0-100	14, 15	S	QLQ-C30
Pain	PA	2	0-100	9, 19	S	QLQ-C30
Dyspnoea	DY	1	0-100	8	S	QLQ-C30
Insomnia	SL	1	0-100	11	S	QLQ-C30
Appetite loss	AP	1	0-100	13	S	QLQ-C30
Constipation	CO	1	0-100	16	S	QLQ-C30
Diarrhea	DI	1	0-100	17	S	QLQ-C30
Financial difficulties	FI	1	0-100	28	S	QLQ-C30

Table 1: Quality of Life Instruments and Scales (continued)

	Scale	Number of items	Score Range	Version 3.0 Item Numbers	Function or Symptom Scales	
Functional Scales			0-100			
Body Image	BRBI	4	0-100	9-12	F	BR23
Sexual Functioning	BRSEF	2	0-100	14, 15	S	BR23
Sexual Enjoyment	BRSEE	1	0-100	16	S	BR23
Future Perspective	BRFU	1	0-100	13	F	BR23
Symptom Scales/Items			0-100			
Systemic therapy side effects	BRST	7	0-100	1-4, 6, 7, 8	S	BR23
Breast Symptoms	BRBS	4	0-100	20-23	S	BR23
Arm Symptoms	BRAS	3	0-100	17, 18, 19	S	BR23
Upset by hair loss	BRHL	1	0-100	5	S	BR23
EQ-5D-5L Health State Summary Score	VAS		-0.595 – 1.000		F	EQ-5D-5L
EQ-5D-5L Index Score	IndexS		0-100		F	EQ-5D-5L

2.1.1. QoL populations

In the 1301 SAP version 2.1 the QoL population was defined as a single population across all the HOA instruments. After the approval of the SAP it was determined that it would be best to define a separate population for each of the subscales. A subject will be included in the population for a particular subscale if they are in the safety population and they had a baseline assessment for that subscale as well as at least one post baseline assessment (up to last dose day +28 days) for the specific subscale. In the analysis dataset there will be a flag for each subscale population.

2.2. QLQ-C30 and BR-23 Scoring

The scoring for QLQ-C30 and BR-23 follows the EORTC QLQ-C30 scoring manual in following link: <https://www.eortc.be/qol/files/SCManualQLQ-C30.pdf>

2.2.1. EQ-5D-5L Scoring

The EQ-5D-5L consists of 6 items: 5 dimensions (mobility, self-care, usual activity, pain/discomfort, and anxiety/depression) and a health state score. Each of the 5 dimensions has 5 levels. The combination of 1 level from each of the 5 dimensions (e.g. 12234) will be used to obtain the health index score.

To obtain EQ-5D-5L Index score, it is necessary to map to a value set from a particular country that has been well established and validated. The EQ-5D-5L cross-walk value set for United Kingdom (UK) will be used in the derivation of health index scores. UK value sets has been used by PUMA studies 3004 and 6201 in alignment with wide utilization of EQ-5D results in UK.

Derivation of the EQ-5D-5L index scores will use the “EQ-5D-5L Crosswalk value sets” link at the following location:

<https://euroqol.org/eq-5d-instruments/eq-5d-5l-about/valuation/crosswalk-index-value-calculator/>

2.3. Assessments on the same date

Multiple assessments on the same date will be averaged so only one score will be used for any subscale for the given date.

2.4. Visit Time Window

Each QoL assessment is mapped to a scheduled visit. The defined visit windows are non-overlapping and cover all possible dates from Baseline through the date of last dose of study drug administration plus 28 days.

2.4.1. Visit windows:

- The Baseline assessment will be the closest assessment on or before the date of first dose of study drug.
- The time window for C3D1 will be first dose date+1 through first dose date +62 days.
- Except Baseline and C3D1, the time window for the rest of visits will be defined as:
 - Start of window: study day of $(1+21*(\# \text{ of cycles})-21)$
 - End of visit window: study day of $(1+21*(\# \text{ of cycles}) +20)$.
 - The target visit day for a scheduled visit is: $(1+21*(\# \text{ of cycles}))$.

The visit time window mapping up to cycle 19 can be found below in reference to Day 1 which is the first dose date (Day 1).

Cycle	Target Day	Start Day	End Day
Baseline	Day 1	< Day 1	Day 1
Cycle 3 Day 1	Day 43	Day 2	Day 63
Cycle 5 Day 1	Day 85	Day 64	Day 105
Cycle 7 Day 1	Day 127	Day 106	Day 147
Cycle 9 Day 1	Day 169	Day 148	Day 189
Cycle 11 Day 1	Day 211	Day 190	Day 231
Cycle 13 Day 1	Day 253	Day 232	Day 273
Cycle 15 Day 1	Day 295	Day 274	Day 315

Cycle	Target Day	Start Day	End Day
Cycle 17 Day 1	Day 337	Day 316	Day 357
Cycle 19 Day 1	Day 379	Day 358	Day 399

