4.2.2 Enrollment and Randomization of Patients to Treatment

Once eligibility is confirmed, patients will be randomized to a treatment group according to the randomization schedule. All patients must commence treatment with investigational products no later than 14 days after randomization. Patients who do not meet the eligibility criteria will not be randomized in the study, but may be rescreened up to two times at the Investigator's discretion.

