4.2.3 Blinding and Breaking the Blind

This is an open-label study.

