stools provided on the diary help to grade the diarrhea as precisely as possible (per NCI CTCAE v.4.0). Also, the daily dose of loperamide (or other anti-diarrheals, if applicable) noted on the diary for patients in the neratinib treatment arm will be reviewed and recorded on the CRF.

Loperamide will be dispensed directly by the site on or before Cycle 1/Day 1 with neratinib. It is very important to initiate treatment with loperamide concomitantly with the first dose of neratinib to minimize occurrence and severity of diarrhea.

Prophylactic dosing instructions (Cycle 1)

- Inform patients that they will experience diarrhea while taking neratinib.
- Administer loperamide: initial dose of 4 mg (2 tablets/capsules) with the first dose of neratinib, followed by 2 mg (1 tablet/capsule) every 4 hours for the first 3 days. After the first 3 days, take loperamide 2 mg every 6 to 8 hours until the end of the first cycle of therapy regardless of whether the patient is experiencing diarrhea or not.
- For patients with persistent Grade 1 diarrhea (<4 stools per day above baseline) on loperamide, Lomotil[®] (diphenoxylate hydrochloride and atropine sulfate) 1 tablet (2.5 mg) every 6 to 8 hours may be added (or equivalent as approved by Sponsor).
- For Grade 2 diarrhea during Cycle 1 (4 to 6 stools per day above baseline, despite intensive anti-diarrheal therapy), consider adding octreotide (short-acting) 150 µg subcutaneous [SC] injection 3 times a day, or after initial dose of short-acting octreotide, if well tolerated, a single dose of octreotide LAR 20 mg by intramuscular injection (equivalent medication may be used with approval of the Sponsor).
- The sites must contact the patient by phone at 1 day, 2 days, and 3 days after the first dose of neratinib to inquire about any diarrhea.

(These phone calls are mandatory and must be recorded in the study chart together with response from the patient and action taken.)

- Instruct patients to promptly report diarrhea symptoms.
- Instruct patient to record the number of stools per day (see Patient Diary, Section 8.5) and the dose of anti-diarrheal medication taken each day (for patients in the neratinib treatment arm) for the first 2 cycles.

For new onset uncomplicated Grade 1 or Grade 2 diarrhea (Cycle 2 and beyond)

Dietetic measures

- Stop all lactose-containing products.
- Drink 8 to 10 large glasses of clear liquids per day.
- Eat frequent small meals.

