9.1 Screening/Baseline

Screening activities are to be conducted within 21 days prior to randomization. Baseline assessments must be done within 72 hours before randomization. Randomization should occur after all baseline assessments have been completed and the site confirms that the patient still meets all eligibility requirements.

The following information and assessments will be performed, collected and/or recorded at screening in accordance with the Schedule of Procedures (Appendix 1):

- Signed ICF for the study.
- Collect demography: date of birth, sex, race (Asian, Black or African American, White, Native Hawaiian or Pacific Islander, American Indian or Alaskan Native, Other), and ethnicity (Hispanic or Latino, Non-Hispanic or Non-Latino).
- Medical history:
 - Record chronic conditions and/or medical history of significance (including the review of history of cardiac, pulmonary and gastrointestinal disease), relevant surgical procedures and symptoms experienced during the previous 30 days as well as those ongoing at the time of screening, and any medical conditions that require medication.
 - Cancer history, including but not limited to: date of first diagnosis, nodal status (based on pathologic assessment of nodes at the time of surgery, either before adjuvant chemotherapy or after completion of neoadjuvant chemotherapy), histology, tumor stage at diagnosis, predictive and prognostic biomarkers, previous chemotherapy/biotherapy/ immunotherapy, previous adjuvant therapy (drug names, start and stop dates, reason for TD), previous radiation, and prior cancer-related surgical therapies.
 - Other previous and concomitant medication will be documented, as described in Section 7.
- Physical examination. Refer to Section 8.2.3.

- Vital signs, height and weight. Refer to Section 8.2.2.
- ECG. Refer to Section 8.2.4.
- LVEF (ECHO or MUGA). Refer to Section 8.2.5.
- ECOG performance status. Refer to Section 8.3.3.
- Serum pregnancy test. Refer to Section 8.2.1.
- Laboratory tests (urine dipstick, hematology and serum chemistry panel). Refer to Section 8.2.1.
- Radiographic (or other appropriate modality for) tumor assessment (RECIST v1.1). Refer to Section 8.1.2.
- In addition, following signing of informed consent, tumor tissue must be prepared and sent for central laboratory confirmation of HER2 expression and hormone receptor status (Refer to Section 8.2.1.1).

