17 APPENDICES

Appendix 1

Table A1.1 Schedule of Procedures

Assessment Time Point									
Study Event	Screening ^a	Baseline	Cycle 1 (21-Day Cycle)			Cycle 2+	Treatment Discontinuation	Safety Follow- up Contact	Long-Term Follow-up
Study Days	Within 21 Days Before Randomization	Within 72 Hours Before Randomization	Day 1	Day 8 (±1 day)	Day 15 (±1 day)	Day 1 (±2 days)	0-3 Days After Last Dose	28 Days After Last Dose (+5 days)	Every 12 Weeks Post TD (±7 days)
Procedures									
Informed Consent ^b	X								
Demographics	X								
Medical, Cancer and Medication History ^c	X								
Physical Examination ^d	X	X ^e				X	X		
Vital Signs, height and weight ^f	X	X ^e		X	X	X	X		
ECG ^g	X					X ^g	X ^g		
ECHO/MUGA ^h	X					X ^h	X		
ECOG Status	X	X ^e				X	X		
Health Outcomes Assessments ⁱ		X ^e				X ⁱ	X		
Concomitant Therapy		Collected continuously throughout study period, including each visit						X	
Adverse Events ^j		Collected continuously throughout study period, including each visit						X	
Cancer Therapy ^k								X	X
HER2/ER/PR status (by central lab) ^l	X ^l								
Serum Pregnancy Test ^m	X								

Assessment Time Point									
Study Event	Screening ^a	Baseline	Cycle 1 (21-Day Cycle)			Cycle 2+	Treatment Discontinuation	Safety Follow- up Contact	Long-Term Follow-up
Study Days	Within 21 Days Before Randomization	Within 72 Hours Before Randomization	Day 1	Day 8 (±1 day)	Day 15 (±1 day)	Day 1 (±2 days)	0-3 Days After Last Dose	28 Days After Last Dose (+5 days)	Every 12 Weeks Post TD (±7 days)
Laboratory									
Hematology Panel ⁿ	X	X ^c				X	X		
Serum Chemistry Panel ^o	X	X ^c				X	X		
Urine Dipstick ^p	X	X ^c							
Efficacy Assessments									
CT/MRI ^{a, i, q}	X					X ⁱ			
Survival ^f								X	X
Drug Administration (1st dose no later than 14 days after randomization)									
Neratinib (Arm A) or Lapatinib (Arm B)			Days 1 - 21 of each cycle						
Capecitabine			Days 1 - 14 of each cycle						
Antidiarrheal Treatment ^s			Prior to Neratinib administration						
Dosing Compliance				X	X	X	X		
PK Sampling at Select Study Centers									
PK Sampling ^t			X		X				

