- a. Screening activities are to be conducted within 21 days before randomization. Tumor scans (CT and MRI) and ECHO/MUGA must be performed within 28 days prior to randomization, and preferably no more than 28 days before initiation of treatment. Randomization should occur after all baseline assessments have been completed and the site confirms that the patient still meets all eligibility requirements.
- b. Informed consent must be obtained before any screening procedures begin.
- c. Collect demographic information, relevant medical history, medical conditions or symptoms experienced during the previous 30 days as well as those ongoing at the time of screening, any medical conditions that require medication, and all prior cancer therapies. Identify the start of current medical conditions by at least the month/year; identify the start of significant preexisting conditions by at least the year.
- d. Full physical exam at screening and brief physical exams at all subsequent time points to assess changes from the screening exam.

- e. Baseline physical exam, vital signs, ECOG status, laboratory assessments, and health outcomes assessments must all be done within 72 hours prior to randomization. However, if screening laboratory assessments and ECOG status were performed within 72 hours before randomization and there were no clinically significant findings, these procedures do not need to be repeated.
- f. Vital signs include pulse, blood pressure (after 5 min rest), and temperature (°C or °F; oral, core [rectal], axillary or tympanic); also measure height (screening only) and weight.
- g. ECGs should be performed at Cycle 3/Day 1, Cycle 6/Day 1 and Day 1 of every 6th subsequent cycle during the active treatment phase. ECG should also be performed at Treatment Discontinuation if not done within the previous 12 weeks. Patients using drugs known to cause QT/QTc prolongation should be monitored closely with serial ECGs at the Investigator's discretion. Refer to [Appendix 6](#) for a summary of drugs known to have a risk of causing QT/QTc prolongation, potentially causing Torsade de Pointes (TdP).
- h. For LVEF during the active treatment phase, MUGA/ECHO should be repeated at Cycle 3/Day 1, Cycle 6/Day 1 and Day 1 of every 6th subsequent cycle. MUGA/ECHO should also be performed at Treatment Discontinuation if not done within the previous 12 weeks.

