8.3.3. Other Efficacy Analyses

8.3.3.1. Health Outcome Assessments

The following health outcomes endpoints will be assessed at Cycle 1 Day 1 of the study (at any time within 24 hours of randomization) and at the end of every 6 weeks (\pm 3 days) starting from Cycle 1 Day1 as indicated in the Schedule of Procedures included in the protocol.

- European Organization for the Research and Treatment of Cancer Quality of Life Questionnaire C-30 (EORTC QLQ-C30), version 3
- EORTC QLQ Breast Cancer Module (BR23)
- The EuroQol (EQ-5D) multi-dimensional health status questionnaire

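### Supplemental SAP 2.4.1 ties the quality-of-life baseline to first dose rather than randomisation, so in this open-label trial a form completed after allocation can serve as baseline

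*SAP*

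**What the plan says.** **Before randomisation.** Protocol 9.1 states: "Baseline assessments must be done within 72 hours before randomization". Appendix 1, note e, names the QoL forms explicitly: "Baseline physical exam, vital signs, ECOG status, laboratory assessments, and health outcomes assessments must all be done within 72 hours prior to randomization". In Table A1.1 the only QoL form before dosing sits in the column headed "Within 72 Hours Before Randomization"; none is scheduled on Cycle 1 Day 1. Protocol 4.1 and SAP 2.2 also place baseline assessments ahead of randomisation.

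**Around randomisation, at Cycle 1 Day 1.** SAP 8.3.3.1 says the QoL endpoints "will be assessed at Cycle 1 Day 1 of the study (at any time within 24 hours of randomization"). It does not say whether the 24 hours run before or after randomisation. The sentence then defers to the protocol's Schedule of Procedures.

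**Relative to first dose.** Supplemental SAP 2.4.1 states: "The Baseline assessment will be the closest assessment on or before the date of first dose of study drug". Its window table gives Baseline a target of Day 1 (the first-dose date), an end of Day 1 and no lower limit. Supplement 2.4.2 favours the form nearest the target day when several fall in one window, and Supplement 2.3 averages forms of the same date. SAP 3 has a general baseline convention that is also tied to first dose.

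**Timing and masking.** Protocol 4.2.2: "All patients must commence treatment with investigational products no later than 14 days after randomization". Protocol 4.2.3: "This is an open-label study".

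**The concern.** A self-reported baseline should be fixed before the patient knows the arm. Between allocation and first dose the arms are already treated differently in one respect, counselling. Protocol 7.1.1 instructs sites as follows: "Inform patients that they will experience diarrhea while taking neratinib". An answer given after that can reflect knowledge of the arm. If the form is completed on Day 1 after dosing, which an on-or-before-the-date rule allows, it can also reflect the drug.

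The baseline score is used throughout the QoL analyses. It is the reference for change from baseline and a covariate in the mixed model (Supplement 2.5.2). It also fixes the response class (2.5.3) and the start and threshold for time to deterioration (2.5.4), and it is the first point and the covariate in the AUC analysis (2.5.5). A baseline score is also a condition for entering each subscale population (2.1.1). Diarrhoea is one of the seven scales chosen for the response, deterioration and AUC analyses.

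**Working it through.** **1. The plan's own windows.** With k = cycle number minus 1, the Supplement's rule gives target = 1 + 21k, start = target − 21 and end = target + 20. Cycle 5: k = 4, target 85, start 64, end 105. Cycle 19: k = 18, target 379, start 358, end 399. Cycle 3 has its own limits, first dose +1 to +62 days, which are Days 2 to 63. All nine post-baseline rows reproduce, which confirms that the table counts from first dose.

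**2. Which form is chosen.** Days are counted from randomisation (day 0), and the gap is the time to first dose. The current rule takes the latest form dated on or before first dose.

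| Gap (days) | Only form: day −2 | Only form: first-dose day | Forms on day −2 and first-dose day | Same two forms, last on or before randomisation date |
|---|---|---|---|---|
| 0 | −2 | 0 | 0 | 0 |
| 1 | −2 | +1 | +1 | −2 |
| 3 | −2 | +3 | +3 | −2 |
| 7 | −2 | +7 | +7 | −2 |
| 14 | −2 | +14 | +14 | −2 |

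A patient with the scheduled form alone is handled correctly. A late-only form is accepted as an ordinary baseline. With two forms of different dates the later one is taken.

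**3. How far the recall period reaches past allocation.** For past-week items and a form k days after randomisation, the share is min(k, 7)/7: 1/7 = 14% at 1 day, 3/7 = 43% at 3 days, and 100% from day 7 to day 14. EQ-5D-5L asks about the same day, so the share is 100% from day 1. These figures measure elapsed time, not bias.

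**4. Time-to-deterioration start.** For a patient with an in-window form and a late form, the start moves by at most 3 + 14 = 17 days. Against the 42-day interval between forms, 17/42 = 40%.

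**5. Size of an arm-level effect.** The documents give no count of late or repeat forms and no shift, so both are assumed. Let f be the share of one arm affected and d a one-directional shift in points. Mean change in that arm moves by f × d. Two equal arms from about 600 patients give 300 per arm; the QoL populations would be somewhat smaller.

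| f (patients of 300) | d | f × d |
|---|---|---|
| 1% (3) | 5 | 0.05 |
| 5% (15) | 10 | 0.5 |
| 20% (60), extreme | 10 | 2.0 |

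In the baseline-adjusted mixed model the shift becomes f × d × b, where b is the slope of the post-baseline score on baseline. With b assumed at 0.4 to 0.8, 0.5 becomes 0.2 to 0.4 and 2.0 becomes 0.8 to 1.6 points. The plan's individual threshold is 10 points, so 0.05 to 0.5 is 0.5% to 5% of it, and 2.0 is 20%. If share and shift are the same in both arms, the between-arm effect is 0.

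**The case against.** The strongest reply is that the plan already requires the form before allocation. Protocol 4.1 and 9.1, Appendix 1 and SAP 2.2 all say so, Protocol 9.1 has randomisation wait for the baseline assessments, and SAP 8.3.3.1 itself defers to the Schedule of Procedures. A form completed only after allocation is therefore a departure from the protocol. SAP 5.2 lists and summarises protocol deviations by type and arm, so it need not go unrecorded. This stands, and it is why few patients are likely to be affected. It does not change the selection rule: once such a form exists, Supplement 2.4.1 uses it. SAP 5.2 does not name QoL timing as a deviation type, and no QoL analysis sets these patients apart.

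A second reply is that a last-value-before-treatment baseline is the SAP's general convention. It also fits a QoL population restricted to dosed patients with windows counted from first dose. That is fair, but SAP 3 lets specific sections depart from its conventions, and every dosed patient also has a randomisation date.

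A third is that the mechanism is speculative. The counselling concerns future diarrhoea, the items ask about the past week or today, and risks are explained to everyone at consent. This stands as a limit on any claim about size or direction.

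A reader might also infer that the Supplement expects repeat baseline forms because it has rules for several forms in a window or on a date. The documents do not support that. Those rules are general, and a scheduled form sharing a window with a discontinuation form is enough to explain the window rule.

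**Conclusion.** The point holds in a limited form, and it is minor. The Supplement's rule can select a form completed after open-label allocation, contrary to the protocol's timing, and prefers it to an earlier pre-randomisation form of a different date. That follows from the text alone.

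Three stronger readings are not supported:

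- **A later form always overrides a valid earlier one.** Forms of the same date are averaged, so displacement needs different dates.
- **The QoL comparison is biased towards one arm.** The number of patients affected and the direction are unknown. The 0.05 to 0.5 point range rests on assumed shares and shifts, all in one direction and in one arm; the 2.0-point figure needs an extreme 20% share for which the documents give no basis.
- **The trial's main conclusions are at risk.** SAP 8.3 makes the QoL tests descriptive. PFS, OS and the alpha allocation are untouched.

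**What to change.** **Supplemental SAP 2.4.1.** Define the QoL baseline as the last assessment on or before the date of randomisation. If there is none, use the latest form dated after randomisation and on or before the first-dose date, and flag it. Report flagged patients by arm and run a sensitivity analysis that excludes them. List any other form dated after randomisation through Day 1, but do not average it into the baseline or treat it as a post-baseline record. Without that last rule it could become a deterioration event or an AUC point, because both analyses use all post-baseline records.

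**SAP 8.3.3.1.** Replace the Cycle 1 Day 1 and 24-hour timing of the first form with the protocol's window of 72 hours before randomisation.

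**Cost.** One date condition, one flag, one sensitivity table and one text edit, using dates already collected. No patient leaves the main QoL analysis. For patients with both forms, time to deterioration starts slightly earlier and includes up to 14 untreated days after randomisation. One gap remains: by date alone, a form completed after allocation on the day of randomisation cannot be told from one completed before it.
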